Appendix 2 Group Sequential Interim Monitoring Plan

Introduction

This plan describes an adaptive study design for the evaluation of rucaparib in patients with locally advanced or metastatic urothelial carcinoma. The adaptive design utilizes interim analyses that allow for early stopping for futility after DMC review of futility analysis of the ITT population, the efficacy for HRD subgroups and all safety analyses.

The trial will enroll 60-200 subjects in a single experimental arm.

Objective response rate by RECIST v1.1 as assessed by the investigator will be summarized for the ITT and HRD-positive populations as well as for the exploratory HRD groups.

Primary Analysis

Let p be the true response rate. The primary analysis compares p to a performance goal of 0.10, and is thus a hypothesis test of

$$H_0 : p \leq 0.10 \quad H_1 : p > 0.10$$

Starting with a noninformative Beta(0.1,0.9) prior on p , the posterior distribution is

$$p|\text{data} \sim \text{Beta}(0.1+Y, 0.9+N-Y)$$

where Y is the observed number of responses and N is the number of complete subjects in the trial. The trial is a success if

$$\Pr(p > 0.10 | \text{data}) > 0.95$$

This threshold maintains type I error at 5%. We consider an alternative threshold (0.935) that increases type I error slightly but obtains greater power for comparison.

Design

The trial sequentially enrolls patients and interim analyses are conducted. At the time of each interim analysis, there will be N patients with a 4-month endpoint and M patients that are incomplete. Let Y be the number of responders among the complete patients.

The model computes p_{\max} , the predictive probability of trial success if the trial is followed to the maximum (targeted) sample size and all patients are followed to completion. Let W_{\max} be the number of eventual responders among the unknown patients (incomplete and currently unenrolled). The distribution of W_{\max} is a BetaBinomial(MAXN-N, 0.1+Y, 0.9+N-Y). The predictive probability p_{\max} is the probability W_{\max} results in trial success when N=200 subjects are complete.

The model indicates trial futility at any interim analysis if $p_{\max} < \text{threshold}$, indicating that there is limited probability that the trial will reach success even at the maximum sample size.

For this study design with N=60 minimum, N=200 maximum, a 5% futility threshold, and interims at N=60 and N=120, the required number of successes to continue is summarized in the table below. For example, in the first row we require 5/60, indicating we must have at least 5 successes out of the first 60 patients (so 5 would continue).

Interim	Minimum to Continue (5% predictive probability)
1 (N=60)	5/60 (8.3%)
2 (N=120)	13/120 (10.8%)

Example Trials

Example trial 1

The trial enrolls until the first interim analysis at N=60 ITT patients complete. At this interim, we have 13/60 (21.7%) responses with 40 patients awaiting follow-up. This result is clearly encouraging compared to a 10% baseline rate. With 140 patients still requiring data, the predictive probability of success on the ITT population is 97.5%, well above the threshold for futility. Response among HRD subgroups is evaluated and the trial continues.

The second interim analysis occurs with N=120 ITT patients complete, obtaining 22/120 (18.3%) with 27 incomplete. Response among HRD subgroups is evaluated. With 80 patients remaining needing follow-up, the predictive probability of success is 99.0%, clearly high and the trial continues.

At N=200, we obtain 37/163 responses (22.7%). This results in a posterior probability greater than 99.99% and a successful trial.

Example Trial 2

The trial enrolls until the first interim analysis at N=60 ITT patients complete. At this interim, we have 3/60 (5%) responses with 40 patients awaiting follow-up. The predictive probability of success at this point is only 0.4%. This is below the threshold for futility for the ITT population. The DMC would examine response among HRD subgroups as well as safety data and make a recommendation to stop the trial or continue. If the trial was stopped at this point, it is assumed that all enrolled patients will continue to be followed.

In that follow-up, the trial ended with 12/100 responses (12%). While greater than 10%, this is insufficient for a successful trial ($\text{Pr}(\text{trmt beats ctrl})=56.7\%$) and the trial would have been very unlikely to meet its primary objective even had N=200 subjects been enrolled.

Example Trial 3

The trial enrolls until the first interim analysis at N=60 ITT patients complete. At this interim, we have 5/60 (8.3%) responses with 40 patients awaiting follow-up. With 140 patients still requiring data, the predictive probability of success on ITT is 5.1%, barely above the threshold for futility. Response among HRD subgroups is evaluated and the trial continues.

The second interim analysis occurs with N=120 complete, obtaining 14/120 (11.7%) with 31 incomplete. With 80 patients remaining needing follow-up, the predictive probability of success is 13.1%, also high enough to continue. Response among HRD subgroups is evaluated and the DMC recommends that the trial continue.

At N=200, we obtain 20/200 responses (10.0%). This results in a posterior probability of 47.5% and a nonsuccessful trial.

Simulations and Operating Characteristics

The operating characteristics of this trial were determined through trial simulation and compared to a potential Simon 2-stage design. We computed the operating characteristics under the assumptions that $p=0.10$ (null hypothesis) and $p=0.11, 0.12, \dots, 0.25$.

A total of 10,000 trials were simulated per scenario. In each, subjects were accrued according to a Poisson process with an average of 1.5 subjects per week. In each simulated trial, interims analyses were conducted according to prespecified rules and the results were recorded.

The detailed results are shown in the following tables for Expected Sample size and for Power, respectively.

Expected Sample Size	$p=0.10$ (null)	$p=0.15$	$p=0.20$	$p=0.25$
Fixed	200.00	200.00	200.00	200.00
Simon	141.52	188.83	204.28	205.92
Adjusted	150.85	192.38	199.60	199.98
Unadjusted	151.60	192.67	199.40	199.99

Pr(trial success)	$p=0.10$ (null)	$p=0.15$	$p=0.20$	$p=0.25$
Fixed	0.043	0.683	0.989	0.999
Simon	0.049	0.673	0.977	0.999
Adjusted	0.062	0.736	0.991	1.000
Unadjusted	0.039	0.675	0.985	0.999

The next table shows the details of if and where each of the adjusted adaptive trial simulations stopped for futility. For each simulated trial, the trial could stop at N=60 complete, N=120, or run to the maximum sample size. Note that trials that stop at N=60 or N=120 complete actually we enroll more than 60 or 120 subjects due to the “overrun”, patients enrolled while waiting for the required patient to complete. In addition, we summarize the probability of a “futility to success flip flop” (FSFF). In actual implementation, when a trial is stopped for futility, you will not get to see what would have happened had you enrolled until N=200. However, in simulation we can simulate those remaining subjects and determine how many futility stops occurred for trials that would ultimately have been successful.

Pr(trial success)	p=0.10 (null)	p=0.15	p=0.20	p=0.25
Futility N=60	0.270	0.042	0.004	0.000
Futility N=120	0.331	0.054	0.000	0.000
Pr(FSFF)	0.004	0.022	0.004	0.000

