9.9 Sample Size Considerations

The overall sample size was determined by considering the number of patients needed for adequate safety and activity assessment of HRD-positive patients. Based on the estimated prevalence of 60% HRD-positive patients in this population, approximately 200 patients will be enrolled into the study. This would result in enrollment of approximately 120 HRD-positive patients. The overall sample size will enable robust estimates of response for the ITT population as well as allow for an exploration to define the optimal HRD signature that correlates with response to rucaparib. The null hypothesis for response rate based on historical data in similar patient populations is $p=0.10$. With a total sample size of 200 patients, the study has greater than 90% power to reject the null hypothesis at a 5% significance level if the true response rate for rucaparib is 20%.

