3.1 Analysis Populations

The following analysis populations are defined for the study:

Safety Population – The safety population will include all patients who received at least 1 dose of rucaparib.

Intent-to-treat Population (ITT) – The ITT population will include all patients who received at least 1 dose of rucaparib.

HRD-positive Population – The HRD-positive population will include all patients who received at least 1 dose of rucaparib and are classified as HRD-positive by the prospectively-defined HRD signature (See [Section 3.2](#)).

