5 PROTOCOL DEVIATIONS

The number of patients with major protocol deviations (eg, inclusion or exclusion criteria) will be determined prior to data base lock and will be summarized with frequencies and percentages or provided in a patient listing.

Protocol deviations will not be used to exclude any patients from the efficacy analyses.

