9.1 Primary Efficacy Analysis

The primary efficacy endpoint of ORR is defined as the proportion of patients with a confirmed response of complete response (CR) or partial response (PR) by RECIST v1.1 ([Appendix 1](#)) as assessed by the investigator. The ORR will be summarized with frequencies and percentages.

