10.5 Interim Analyses and Data Monitoring

A group sequential interim monitoring plan will be implemented in order to help guide the data monitoring committee (DMC) in monitoring the study. The null hypothesis is $p=0.10$ based on historical data in similar patient populations. The study has greater than 90% power to reject the null hypothesis at a 5% significance level if the true response rate for rucaparib is 20%.

Interim analyses will be performed when approximately 60 patients and 120 patients have complete data, defined as a documented response (PR or CR), disease progression, or at least 4 months of disease assessment data available.

If the response rate does not meet continuance criteria for the ITT population, the DMC will further evaluate the benefit: risk for study treatment, both overall and separately for patients in different HRD subgroups, and make a recommendation whether further enrollment into 1 or all groups should be discontinued.

Additional details regarding this group sequential interim monitoring plan are provided in [Appendix 2](#).

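### The success test counts complete subjects while the primary ORR counts all dosed patients; the plan mostly implies all dosed, but the wording can decide a borderline result

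*SAP*

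**What the plan says.** The only success rule is in SAP Appendix 2, repeated in Protocol Appendix 4. With a Beta(0.1, 0.9) prior, the posterior is Beta(0.1+Y, 0.9+N−Y), where "Y is the observed number of responses and N is the number of complete subjects in the trial". Success requires Pr(p > 0.10 | data) > 0.95, and the appendix states that this holds type I error at 5%.

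SAP 10.5 and Protocol 9.10 time the interims by the number of patients with "complete data, defined as a documented response (PR or CR), disease progression, or at least 4 months of disease assessment data available". No other definition of complete is given.

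The SAP body uses a different base. Section 9 runs efficacy on the ITT and HRD-positive populations, and in section 3.1 "The ITT population will include all patients who received at least 1 dose of rucaparib". Section 9.1 defines ORR as "the proportion of patients with a confirmed response of complete response (CR) or partial response (PR) by RECIST v1.1". Section 5 adds: "Protocol deviations will not be used to exclude any patients from the efficacy analyses". Section 10.1 rules out imputation.

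The appendix also contains wording that fits all dosed patients. The predictive probability is the chance that the remaining data "results in trial success when N=200 subjects are complete", and Examples 1 and 3 describe it as success on ITT. Protocol 9.9 states: "With a total sample size of 200 patients, the study has greater than 90% power to reject the null hypothesis".

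**The concern.** The literal test and the primary ORR can have different denominators. A patient with a documented response is complete by definition, so incomplete patients can only be non-responders. Removing them from N raises the tested rate and can lower the number of responders needed.

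Such patients are foreseeable from the protocol. Eligibility asks for a life expectancy of at least 12 weeks, which is shorter than 4 months. The first on-treatment scan is due at 8 weeks. Treatment may stop for clinical progression without radiologic progression, and under Protocol 7.5.3 scanning stops once subsequent treatment begins.

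What is at stake is whether a close result is called a success, and whether the stated 5% refers to the ITT rate. In an open-label single-arm study this should be settled before the data are seen.

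**Working it through.** **Inputs.** Prior, threshold and 10% null: SAP Appendix 2. Planned size 200: Protocol 9.9, SAP 2.3. The proportion incomplete, d, is given nowhere; it is assumed at 0% to 10%, with incomplete patients as non-responders.

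**1. Reproduce the plan.** Find the smallest Y with Pr(p > 0.10 | Beta(0.1+Y, 0.9+N−Y)) > 0.95.
- N = 200: Y = 27 gives 0.9355 and Y = 28 gives 0.9585, so the bar is 28.
- P(Bin(200, 0.10) ≥ 28) = 0.0434; printed 0.043 (Fixed row).
- P(Bin(200, 0.20) ≥ 28) = 0.989; printed 0.989.
- Predictive probabilities with a final N of 200 and bar 28: 13/60 gives 97.55%, 3/60 gives 0.36%, 5/60 gives 5.07%, 22/120 gives 99.0% and 14/120 gives 13.14%. These match the printed 97.5%, 0.4%, 5.1%, 99.0% and 13.1% to rounding.

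The printed operating characteristics therefore take all 200 patients into N.

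**2. Effect of dropping incomplete patients.** The bar is 28 for N = 196 to 200, 27 for N = 187 to 195 and 26 for N = 179 to 186. Four incomplete patients of 200 change nothing (27/196 gives 0.9474). Five lower the bar to 27 (27/195 gives 0.95004).

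**3. Type I error on the literal reading.** The number incomplete is Bin(200, d). For each resulting N, take the binomial tail at that N's bar, with response probability 0.10 if the null is the rate among complete patients, or 0.10/(1−d) if it is the ITT rate. Each cell shows the result without stops / with binding futility stops at 5/60 and 13/120.

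| d (assumed) | Null = rate among complete | Null = ITT rate |
|---|---|---|
| 0% | 4.3% / 4.2% | 4.3% / 4.2% |
| 1% | 4.0% / 3.8% | 4.5% / 4.3% |
| 2% | 4.2% / 4.0% | 5.2% / 5.0% |
| 3% | 4.4% / 4.2% | 6.0% / 5.7% |
| 5% | 4.2% / 4.1% | 7.0% / 6.8% |
| 10% | 4.2% / 4.1% | 11.2% / 10.9% |

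In the last column 5% is passed near d = 1.9% without stops and 2.1% with stops. With exactly five of 200 incomplete, the ITT-null figure is P(Bin(200, 0.10) ≥ 27) = 6.7%.

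**4. All dosed patients in N.** With exactly 200 dosed: bar 28, type I error 4.3%, power 98.9% at a 20% rate. Enrolment is only approximately 200, and the bar moves in whole patients: 195 dosed gives bar 27 and 5.2%; 203 dosed gives bar 28 and 5.1%.

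**5. Worked examples.**
- Example 3: 20/200 gives 47.5%, as printed.
- Example 1 prints 37/163 at N = 200 with a posterior above 99.99%. 37/163 gives 99.9999%; 37/200 gives 99.98% and an ORR of 18.5%, not 22.7%. Note that 37 + 163 = 200.
- Example 2 prints 12/100 with 56.7%. The formula gives 71.4% for 12/100 and 56.65% for 12/112 (12 + 100 = 112). The 100 itself is the 60 complete plus the 40 awaiting follow-up.

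**The case against.** The strongest reply is that the documents already settle the denominator. The SAP body analyses ITT. A dosed patient without a confirmed response is in the ORR denominator and not in the numerator, so early deaths and losses do have a status there. Completeness is defined only to time the interims; at the end it can simply mean that follow-up has finished. Example 2's 100 is every patient enrolled by then, which supports an all-enrolled base. This largely stands, and it confines the gap to the posterior test and the interim counts. It does not remove the gap, because the appendix defines N otherwise and nothing limits that definition to the interims.

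A reader might infer that the 5% error control is lost. The documents do not support that. If N is complete patients, the binomial model most naturally makes p, and hence the null, the rate among complete patients, and average type I error stays below 5%. The higher figures combine a complete-patient N with an ITT null and need a loss rate that no document gives.

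A reader might also take 37/163 as proof that 37 patients were dropped. The printed posterior fits 163, but the sum to 200 fits equally well with non-responders having been printed as the denominator. Neither explanation can be confirmed, and 37 responders succeed on either base.

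Finally, 27/195 clears the threshold very narrowly, and part of this step is ordinary binomial discreteness, which an ITT denominator has too. That is correct, and it is why the bar should be tied to the actual number dosed.

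**Conclusion.** This is a specification gap in the success test, of minor to should-fix severity. The plan's sample size and power figures are not wrong: they reproduce with all 200 patients in N, which is probably what was intended. As written, the appendices allow a denominator that omits only non-responders, and five such patients are enough to turn 27 responders from failure into success.

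The size of the error effect depends on two things that the plan does not state. If the 10% null is the complete-patient rate, type I error is 4.0% to 4.4% without stops for assumed losses up to 10%. If it is the ITT rate, it exceeds 5% from about 2% incomplete and is 7.0% at 5% incomplete. With four or fewer of 200 incomplete the bar does not move. The descriptive ITT ORR is not in doubt.

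**What to change.** In SAP Appendix 2 and Protocol Appendix 4, define N at the final analysis as all dosed (ITT) patients, and count any dosed patient without a confirmed response per SAP 9.1 as a non-responder. State in SAP 10.5 and Protocol 9.10 that completeness governs interim timing only. Say that the bar is recomputed from the actual number dosed (28 if exactly 200) and acknowledge that type I error can then sit slightly above 5% at some sizes, such as 5.2% at 195 and 5.1% at 203.

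Verify and correct Example 1 (37/163 against 37/200) and Example 2 (71.4% for 12/100, or the inputs that give 56.7%).

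Counting early losses as complete non-responders at the interims is optional and should be checked before adoption: 5/60 continues at 5.07%, but adding three early losses makes it 5/63, which falls to 3.5% and below the 5% futility threshold.

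The cost is a few sentences in each document, with no extra patients or data. With 200 dosed, the bar and stated operating characteristics do not change. The downside is a slightly less favourable tested response rate if some patients are incomplete.
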